6.3 Stopping Points

The patient's physician or the principal investigator may withdraw the patient from the study for any reason. An End of Study form will be completed with the reason for withdrawal documented in such an occurrence.

The study drug will be permanently discontinued in one of the following circumstances:

- The participant meets an exclusion criteria (either newly developed or not recognized previously) that precludes further study participation
- The patient has been on study drug or received placebo medication for 30 days from the date of study drug activation
- The patient's platelet count increases spontaneously from $<30,000/\mu\text{L}$ to $\geq 50,000/\mu\text{L}$ across two successive platelet measurements with no intervening platelet transfusion
- The patient's platelet count remains $\geq 30,000/\mu\text{L}$ on 2 measurements made at least 46 hours apart without intervening platelet count of $<30,000/\mu\text{L}$ or a decrease in platelet of greater than 50% between two measurements and without intervening platelet transfusion
- The patient is prescribed any other procoagulant, antiplatelet or anticoagulant agent by their treating physician (this includes open label tranexamic acid)
- The patient is discharged from hospital admission
- The patient experiences a thrombotic event
- The patient develops sinusoidal obstructive disease
- The patient develops visible hematuria, renal dysfunction (as defined in Section 6, table 2) or anuria
- The patient has a recurrent incident of complete central line occlusion: defined as the inability to access or infuse through a central line requiring instillation of fibrinolytic agent such as alteplase for clearing. This does not include lines that require certain patient positioning for instillation of agents, which suggest a "kink" in the line. A recurrent incident is when the definition is met on 2 separate occasions while receiving study drug.
- The patient becomes pregnant

If any of the above reasons lead to cessation of the study drug it should not be restarted even if the patient later meets criteria again for the study drug.

Subjects have the right to withdraw consent at any time. If a patient withdraws their consent for further participation, the subject will be asked to grant consent for the study

team to passively monitor their outcomes for major clinical events. For each patient at the end of therapy, the date and time that the study drug is voluntarily stopped will be recorded, along with the reasons that the subject so elected. It will be documented whether the subject is:

- Stopping study drug, but will continue to follow all other study-defined procedures and monitoring
- Stopping study drug and study-defined procedures and monitoring but allows investigators to passively monitor their medical record and follow-up for vital status up to 30 days after their last dose of study drug.
- Discontinuing all further contact with study investigators

In the event of subject death, the date of death will be recorded on the study form and will be characterized by time from consent and according to whether the investigator attributes the mortality to bleeding, thrombosis or death from other cause.

When a patient meets one of the above study stopping criteria, the study medication will be discontinued following the next daily assessment.

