6.2 Concomitant Care

Patients enrolled on trial must have a prophylactic platelet transfusion threshold of $\leq 10,000/\mu\text{L}$ (for patients with solid tumors or hematologic malignancies not undergoing BMT) or $\leq 20,000/\mu\text{L}$ (for patients undergoing BMT) at the time of randomization. Prophylactic platelet transfusions will be given when morning platelet count is below the above values for prophylactic transfusions. Therapeutic platelet transfusions above these thresholds will be allowed at the discretion of their treating physician (for cases including active bleeding, for an expected platelet count of $\leq 10,000$ or $\leq 20,000/\mu\text{L}$ the following morning, planned invasive procedures with the need for an increased platelet threshold or trauma). Clinicians will be allowed to exercise discretion to transfuse platelets for any reason should they feel there is a clinical reason to do so. In cases where a platelet transfusion is given for invasive procedures or trauma the subject will return to the study platelet transfusion threshold following this event when determined safe to do so by the treating physician. If, following enrollment and study drug activation, the subject subsequently has an event which leads to the need for a platelet transfusion threshold of greater than the study protocol, they will remain on study.

Type and dose of platelet transfusion will not be specified. If a patient appears to develop platelet refractoriness (which is defined as two sequential transfusions with a repeat platelet count after a 4hour period of $\leq 5000/\mu\text{L}$) then clinicians may exercise their judgement as to use of matched platelets or alloantibody testing. Data on type of platelet transfusion administered will be collected. For any platelet transfusions given

above the study threshold the rationale will be recorded on the daily transfusion assessment form.

Patients will receive red blood cell transfusions as per the standard care of their treating physician.

No other medication changes are directed in this protocol and standard care will otherwise be followed.

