11.1.2 Secondary Endpoints

- Assessment of the effect of tranexamic acid on bleeding will consider the difference in the proportion of patients experiencing WHO Grade 2 or higher bleeding between the two study arms following activation of the study drug and until study drug cessation, the proportion of patients with any grade bleeding event following activation of study drug, the highest grade of bleeding experienced during study period and the length of time from study drug activation to WHO Grade 2 or higher bleeding event
- Assessment of the effect of tranexamic acid on platelet transfusion requirement will consider the difference in the number of platelet transfusions administered per patient between the study arms following activation of the study drug and until study drug cessation.

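### In 6.3 the 46-hour platelet stop can be met by falling post-transfusion counts: it does not address a transfusion before the first count, and its 50% guard acts only above 60,000/uL

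*Combined protocol and SAP*

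**What the plan says.** Section 6.3 has two permanent stops based on platelet recovery.

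- The first applies when the "platelet count increases spontaneously from" below 30,000/uL to 50,000/uL or more, "across two successive platelet measurements with no intervening platelet transfusion".
- The second applies when the "platelet count remains $\geq 30,000/\mu\text{L}$ on 2 measurements made at least 46 hours apart", provided that no count in between is below 30,000 and subject to the further condition "or a decrease in platelet of greater than 50% between two measurements and without intervening platelet transfusion".

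After either stop, "it should not be restarted even if the patient later meets criteria again for the study drug". Section 6.3 also says that drug is discontinued after the next daily assessment and asks for no re-check of the count. Section 6.4 allows a temporary stop only for DIC and a first central line occlusion.

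On transfusion, 6.2 sets prophylactic thresholds of 10,000/uL (20,000/uL for BMT) and adds: "Clinicians will be allowed to exercise discretion to transfuse platelets for any reason". It also states: "Type and dose of platelet transfusion will not be specified". Section 8.5 requires a CBC every day on study drug and daily transfusion data with reasons. Section 5.2 activates study drug at 30,000/uL or below.

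**The concern.** The second bullet appears meant to identify platelet recovery that is not a transfusion effect, but it protects only the interval between the two counts. A transfusion given just before the first count raises both. The 50% condition looks like the safeguard against this, since transfused platelets decay, yet the 30,000 floor leaves it little room to act. The word spontaneously, which would have covered the case, stands only in the first bullet.

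At stake is study drug exposure in a trial with a target of 10 activated patients per arm (5.3), where each such stop is 1/10 = 10% of an arm. A patient whose counts are still falling can be recorded as recovered, lose the remaining treatment days, and be barred from restarting when the count returns to the activation level. Under 11.1.2, bleeding and platelet transfusions are counted "following activation of the study drug and until study drug cessation", so these endpoints would be cut short as well.

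**Working it through.** The plan states no figure on this point, so there is none to reproduce. The check is of the rule itself.

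**1. When the 50% condition can act.** Let A be the earlier count and B the later one. The stop needs B ≥ 30,000. The condition blocks it only if B < A/2. Both hold only if A/2 > 30,000, that is A > 60,000.

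| Earlier count A | Largest fall the floor allows, 1 − 30,000/A | Can the condition act? |
|---|---|---|
| 40,000 | 25.0% | no |
| 50,000 | 40.0% | no |
| 60,000 | 50.0% (not more than 50%) | no |
| 61,000 | 50.8% | yes |

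Enumerating every triple of daily counts from 30,000 to 60,000 in steps of 500 (61³ = 226,981) gave no case that the condition blocked. Reading it as first count against last, or as any pair of counts, gives the same limit.

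**2. Falling sequences that meet the stop** (counts at 0, 24 and 48 h, transfusion just before 0 h, none afterwards):

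- 50,000 / 40,000 / 32,000: fall 1 − 32/50 = 36.0%.
- 58,000 / 43,000 / 31,000: fall 1 − 31/58 = 46.6%.
- 70,000 / 50,000 / 36,000: fall 1 − 36/70 = 48.6%. The gap is therefore not confined to counts at or below 60,000.

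The same transfusion given just after the 0 h count would block the stop. The outcome turns on the order of transfusion and blood draw, not on the marrow.

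**3. How often.** This needs the transfusion increment and platelet survival, and the documents give neither. As an assumption only, take exponential decay with mean life L days. The first count needed to be at 30,000 after 46 h is 30,000 × exp(46/(24L)): about 56,800, 48,400 and 44,000 for L = 3, 4 and 5.

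Simulated patients who never recover (daily counts, transfusion at the 6.2 trigger, increment SD 35%, start at 25,000) meet the stop within 30 days in anything from near 0% to near 100%, depending on the assumed increment and survival. The result also turns on a bookkeeping choice. With a 30,000 increment, 4-day life and the 20,000 trigger it is about 40% if the increment decays for a day before the next morning count, and about 90% if it is credited in full at that count. This model cannot test the 50% condition: its largest 48 h fall is 1 − exp(−2/3) = 48.7%, at L = 3.

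**4. Timing.** Activation needs a count of 30,000 or below. With morning counts and a transfusion on Day 1, the first qualifying count is on Day 2 and the second on Day 4, and drug stops after the next assessment. No simulated stop was met by Day 4.

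**5. Endpoint windows.** Section 11.1.2 ends bleeding and platelet-transfusion counting at cessation. Section 11.3 runs efficacy data to discharge or 30 days after activation, whichever is sooner. Section 11.5 follows all clinical outcomes regardless of adherence. Section 3.3 collects adverse events to 30 days after the last dose.

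**The case against.** The two bullets are alternative triggers, not rival definitions. The first acts on a jump between successive counts, so it needs a word such as spontaneously. The second acts on persistence, and at least 46 hours at or above 30,000 with no transfusion is itself a guard. Whether that is long enough is a clinical design judgement. This largely stands: there is no strict logical contradiction, and this review takes no position on the interval. What it does not answer is that the second bullet is silent on a transfusion before the first count, and that its 50% condition is inactive over part of the range to which the rule applies.

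A reader might also infer stronger consequences, which the documents do not support:

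- **That such stops will be common, or more common in BMT patients.** No increment or survival is given, and 6.2 anticipates refractoriness, so no percentage can be relied on.
- **That an arm difference in bleeding or transfusion will shrink.** No bleeding process by arm was modelled, and 11.3 and 11.5 limit the truncation that 11.1.2 implies. Bleeding is a secondary aim for which 11.7 concedes inadequate power.
- **That the steady-state fibrinolysis sample will be lost.** The Day 4-6 window in 8.7 is usually open before the stop takes effect. Loss is possible, not typical.
- **That safety follow-up ends.** Exposure shortens, but adverse event collection continues under 3.3.

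**Conclusion.** The point holds in a limited form. As written, the second platelet stop in 6.3 can classify falling, transfused counts as recovery and end study drug irreversibly; neither 6.4 nor the delay to the next daily assessment rescues the patient. That the 50% condition acts only above 60,000/uL follows from the rule's own figures and needs no assumption. The sequences above show that the stop can be met, not how often it will be: any frequency rests on assumed increments and survival and spans almost the whole range. The effect on bleeding and platelet-transfusion endpoints depends on whether 11.1.2 or 11.3 governs the window. It should be corrected, because following the rule exactly can give a result contrary to its evident aim and the correction is cheap.

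**What to change.** The investigators should reconcile the two platelet-recovery bullets of 6.3, including the 50% condition, with each other and with the aim of identifying recovery that is not due to transfusion. The choice of rule is theirs, and none is proposed here.

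From the daily CBC and transfusion data already collected under 8.5, tabulate by arm how many platelet-recovery stops followed a recent platelet transfusion, and report these separately from untransfused recovery. The investigators should define recent before unblinding.

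The cost is a small wording amendment and one extra table, with no new data collection. Some patients may stay on study drug longer, within the existing 30-day cap.

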3.3 Safety Endpoints

Adverse events and serious adverse events will be monitored and collected from the time of activation of the study drug until a period up to and including 30 days after the last dose of the study drug. Adverse events and serious adverse events will to be assessed by CTCAE v.4.0 criteria and compared between study drug and placebo arms. The following events will specifically be compared across study arms;

- Incidence of thrombotic events (A thrombotic event is defined as venous or arterial thrombosis confirmed on imaging study, which may include Doppler US, CT scan, MRI or venography)
- Incidence of veno-occlusive disease (also known as sinusoidal obstruction syndrome)
- All cause-mortality, including incidence of death due to thrombosis

4. Population

Pediatric patients with hematologic malignancy or solid tumors receiving chemotherapy or undergoing BMT.

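### Section 6.3 times every permanent stop to the next daily assessment, so doses may continue after a safety stop is recognised between assessments

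*Combined protocol and SAP*

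**What the plan says.** Section 6.3 opens its list of permanent stops with "The study drug will be permanently discontinued in one of the following circumstances", which gives no timing. The list mixes two kinds of stop.

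- **Safety stops.** These include "The patient experiences a thrombotic event", "The patient develops visible hematuria, renal dysfunction (as defined in Section 6, table 2) or anuria" and "The patient is prescribed any other procoagulant, antiplatelet or anticoagulant agent by their treating physician (this includes open label tranexamic acid"). Sinusoidal obstruction, recurrent complete line occlusion, pregnancy and any newly developed exclusion criterion that rules out further participation are also listed.
- **Administrative or recovery stops.** These are 30 days on study drug, two forms of platelet recovery, and discharge.

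The section then closes with one timing rule for the whole list: "When a patient meets one of the above study stopping criteria, the study medication will be discontinued following the next daily assessment".

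Section 6.4 adds two temporary stops, DIC and a first line occlusion, with no timing.

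**The concern.** Waiting for the next assessment is reasonable for platelet recovery, where another dose or two does little harm. It is a poor default for events that the protocol treats as reasons not to give an antifibrinolytic. Section 9.4 itself warns of ureteral obstruction by clot in patients with upper urinary tract bleeding, of thromboembolic events, and of convulsions. The protocol also lists anaphylactic shock as a rare but important effect.

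At stake is patient safety in the tranexamic acid arm, not the analysis. Care providers are blinded (7.1), so they cannot tell whether the next scheduled dose is active drug. A nurse or physician who follows 6.3 literally could give that dose after the reason to stop is known.

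**Working it through.** The plan gives no figure on this point, so there is none to reproduce. The check has three parts.

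**1. Does any section require an earlier stop?**

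| Section | What it provides | Immediate stop required? |
|---|---|---|
| 6.3, lead-in | Permanent discontinuation, untimed | No |
| 6.3, closing sentence | Stop after the next daily assessment | No; it sets the delay |
| 6.3 and 10.2 | Physician or investigator "may withdraw the patient from the study for any reason"; subject may stop at any time | No; discretionary |
| 6.4 | Temporary stops, untimed | No |
| 7.2, 8.4, 8.5 | Administration and daily procedures | No |
| 9.1 | Investigator reviews safety data as they arise | No; review, not a dosing action |
| 9.4 and 9.4.1 | Bars use with Factor IX complex and anti-inhibitor coagulant concentrates; advises against contraceptive estrogens and progestins | Only for those agents |
| 10.3 | Discharge day is the last treatment day | Discharge only |

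No section requires an immediate stop for thrombosis, visible hematuria, a new antiplatelet, anticoagulant or open-label tranexamic acid, seizure or allergy.

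**2. Can these be recognised between assessments?**

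- *Thrombosis.* Section 3.3 says "A thrombotic event is defined as venous or arterial thrombosis confirmed on imaging study". Under 8.10, study staff look back over imaging done since the previous assessment. The treating team can therefore have the result first.
- *Interacting agents.* The treating physician prescribes them, so the stop can arise outside any study visit.
- *Visible hematuria, seizure, allergic reaction.* These can be seen at the bedside at any hour. Seizure history and tranexamic acid allergy are exclusions in 4.2, so a new occurrence falls under 6.3.

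**3. How many doses can follow?**

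Inputs:
- Dose *d* = 10 mg/kg every 8 h, or TID (6.1, 7.2).
- Assessments are daily, with no clock time set (8.5, 11.3).
- Assumed gap between assessments *G* = 24 h.

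Results:
- Maximum doses, every 8 h: *G* / 8 h = 24 / 8 = 3.
- Maximum doses, TID at fixed clock times: 3 in any 24 h.
- Maximum exposure: 3 × 10 mg/kg = 30 mg/kg.
- Minimum: 0, if no dose falls due before the assessment, or if the criterion is found and acted on at the assessment.
- Under every-8-h dosing, each further 8 h between assessments would add one dose.
- With a rule of no dose after recognition: 0 doses, 0 mg/kg.

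**The case against.** The best answer is that clinicians would stop anyway. The list is mandatory, these are inpatients under close care, and a treating team that knows of a confirmed clot has express authority to withdraw the patient. That lowers the likelihood of harm. It does not remove the gap, because the authority is permissive and is framed as withdrawal from the study rather than a drug stop. A clinician who withholds the dose would be departing from the written rule.

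Three limits stand in full.

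- **Not every safety stop is equally exposed.** Creatinine is drawn daily (8.5), so renal dysfunction will mostly surface on the daily cycle. Anuria is defined over 24 hours (4.2). A completely occluded line cannot carry the dose until it is cleared. For pregnancy, no test is scheduled after randomization, so detection matters more than a delay of about a day.
- **Some procoagulants have their own instruction** in 9.4 and 9.4.1, as tabulated above.
- **The dose is modest and the trial small.** Section 6.1 places the dose in the low range of recommended pediatric intravenous doses, and 5.3 targets 10 activated subjects on tranexamic acid.

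A reader might also infer that the closing sentence carries dosing past day 30, because "The patient has been on study drug or received placebo medication for 30 days from the date of study drug activation" is one of the listed criteria. The documents do not support this. Section 8.5 and Table 3 schedule study drug and daily assessments only through Day 30, so no later daily assessment exists to extend treatment.

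**Conclusion.** The concern holds as a wording gap with a safety consequence. Section 6.3 states a single timing rule that, followed literally, allows 0 to 3 further doses (up to 30 mg/kg in the tranexamic acid arm) after a safety criterion is recognised between assessments. It matters chiefly for imaging-confirmed thrombosis, visible hematuria, newly prescribed interacting agents, and new exclusions such as seizure or tranexamic acid allergy.

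The range rests on assessments 24 h apart, which the protocol does not fix. A reader might want an average number of extra doses or an expected number of affected patients. The documents support neither: they give no event rates, no assessment times and no distribution of recognition times. Nor does the sentence compel further dosing; it permits it. The gap should be closed because it is avoidable and cheap to close. Nothing in the documents shows that it would arise often.

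**What to change.** Replace the closing sentence of 6.3 with wording such as:

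> No further dose of study drug will be given once a safety stopping criterion (any criterion in 6.3 other than platelet recovery, day 30 or discharge) is recognised by the treating team or study staff. For the platelet-recovery criteria, study drug stops after the next daily assessment.

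Add the same no-further-dose wording to 6.4 for DIC and a first line occlusion, leaving restart after resolution as it is. Day 30 and discharge need no new text, because 8.5 and 10.3 already govern them.

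Defining the safety group by exception avoids a second list and leaves no newly met exclusion, such as TTP or HUS, under the delayed rule. The change alters when a stop takes effect, not which events are stops.

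The cost is one reworded sentence in 6.3, one added clause in 6.4, and a short instruction to nursing and treating staff. No endpoint, sample size or analysis changes. Section 11.5 already follows patients for clinical outcomes whether or not they keep to the regimen, so an earlier stop need lose no data.

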6.4 Temporary Stopping Points

The study drug will be temporarily discontinued in the following situations:

- Diagnosis of DIC by the treating team or treating physician
- First event of central line occlusion (as defined above)

In these situations, as detailed above, the study drug may be restarted after resolution of the situation.

